- 1) Investigate whether ageing has an effect on baseline CRM skills of ACPs, (emergency, critical care, anesthesia) using simulated crisis scenarios and
- 2) Assess whether ageing influences learning from high fidelity simulation.

We hypothesize that:

1) ACP baseline simulated CRM performance will decline with increasing age,

2) Although all ACP performance will improve at the immediate post-test, increasing age will be negatively impact the retention of CRM skills 3 months following a high-fidelity simulation-based education session.

Methods

Study Design

This study is a prospective cohort multicenter study. Ethical approval will be sought from the Ottawa Health Science Network Research Ethics Board & Sunnybrook Research Ethics Board (Toronto, Canada). Written informed consent and a confidentiality agreement will be obtained from all participants. ACP from the academic affiliated sites of both universities will be recruited, with data collection being conducted locally in each city.

Recruitment and orientation

Practicing emergency, critical care and anesthesia staff with a minimum 5 years of practice post residency will be approached for participation.

The participants will take part in three 8-minute simulated crisis scenarios based on current Advance Cardiac Life Support (ACLS) guidelines for pulseless electrical activity (PEA) arrests. The scenarios will serve as pre, immediate post and retention tests. These scenarios will be identical for pediatric anesthesiologists, however the "patient" in the scenario will be of 15 years of age, rather than an adult. Although all three scenarios will ultimately result in PEA arrests, each will have a unique inciting event and these will be randomly assigned. Participants will be unaware as to which scenarios they will be asked to manage. All scenarios will be recorded. Confederates will serve as the patient's nurse and respiratory technician to be directed by the participant, but they will not provide tips or guidance in terms of how to manage the crisis.

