A standardized structured orientation session will be held for all participants. During this session, the principles of simulation-based education will be discussed and the participants will be exposed to the simulation room, all equipment and simulators. Since participants will likely have various types of previous simulation experience, each participant will be familiarized with the simulator by participating in an introductory noncrisis scenario that will not require crisis resource management skills. The scenario will be an induction of general anesthesia using a rapid sequence induction (a common technique for the three acute care specialties in this study). Participants will also complete two questionnaires collecting demographic data (Appendix A), quantifying previous simulation and crisis management experience, and a life expectancy questionnaire online to calculate their "health age". The online questionnaire consists of questions that evaluate physiological and lifestyle factors contributing to one's "health age" and will calculate a person's "health age" based on responses. The participant will record their health age on the demographic questionnaire (Appendix A).

Scenarios

Each participant will then manage a PEA arrest scenario (pre-test) and then be debriefed on their CRM skills by a trained facilitator for 20 minutes. They will then manage another crisis scenario (PEA arrest once again, but with a different inciting event) as an immediate post-test. Three months after completing the instructional session, participants will return to manage a third PEA arrest scenario, which will serve as a retention post-test in additional to completing a retention questionnaire (Appendix D). The retention posttest can be completed up to 6 months following the initial pre-test. All three scenarios will be designed with the same clinical scenario that is common to all ACPs but the physical simulation environment will be set-up according to their specific specialty (i.e. ICU, OR, and ER) so that they are familiar with their unique layouts. All debrief sessions will be recorded as a quality control measure to ensure that all debriefs are conducted in a consistent manner.

Simulation Scenario Development

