The core concepts pertaining to CRM skills and subsequent management of PEA arrest will be consolidated by the principal investigators and then sent out to three faculty acute care physicians (one from each specialty involved) from Universities not involved in the recruitment, who are trained ACLS instructors, for review and revisions. Once core concepts are agreed upon, the three simulation scenarios will be developed. Each scenario will then be piloted before recruitment.

Outcome measures:

As our primary outcome, we will assess the relationship of age with:

A) CRM skills, as measured by (Appendices B & C):

- a. Ottawa GRS scale total score (non-technical CRM skills)²⁴
- b. official ACLS checklist for PEA (technical CRM skills)²⁵

B) Learning* from high-fidelity simulation based education, as measured by change in performance (Appendices B & C):

1) official ACLS checklist for PEA²⁵,

2) Ottawa Global Rating Scale for CRM²⁴

* Learning defined as improvement in performance in the simulation based crisis scenarios.

Two raters blinded to the study hypotheses and the scenarios order (pre vs immediate post vs retention post-test), will evaluate the videos using the above validated tools.

Statistical Analysis and Sample Size Calculation

To test the first hypothesis, a multivariate regression analysis will be performed, with age as a predictor and outcomes A (listed above) as the dependent variables. To test the second hypothesis, a second multivariate regression analysis will be performed with age, pre-test score, post-test scores and their interactions (age x pre-test score, age x intervention, age x pre-test score x intervention, and pre-test score x intervention) as predictors, and outcomes B on the retention test (listed above) as the dependent variables.

To adequately power our study, we will need at least 10 participants per predictor variable entered into the analysis. In order to collect a meaningful sample, we will aim to recruit 10 participants per 10 year age group (<45, 45-54, 55-64, 65+), equaling 40 ACP. To account for attrition, we will aim to recruit 70 participants total across both sites.

Timeline

This study will run for 2 years:	
Ethics Submission:	Months 1-3
Content Development & Pilot Scenarios:	Months 3-4
Data Collection:	Months 5-15
Statistical Analysis:	Months 16-17
Manuscript & Dissemination of results:	Months 18-24

Dissemination Strategy

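### The baseline age model omits specialty, although three specialties are tested in their own rooms and recruitment is balanced by age band only; adjusting for it is a cheap, minor improvement.

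*Combined protocol and SAP*

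**What the plan says.** Under Recruitment and orientation, those approached are "Practicing emergency, critical care and anesthesia staff with a minimum 5 years of practice post residency". Under Scenarios, the room "will be set-up according to their specific specialty", that is ICU, OR or ER, so that the layout is familiar. The same section says "All three scenarios will be designed with the same clinical scenario that is common to all ACPs". Within anesthesia, pediatric anesthesiologists meet a 15-year-old patient instead of an adult.

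Under Statistical Analysis and Sample Size Calculation, the baseline regression is specified "with age as a predictor and outcomes A (listed above) as the dependent variables". For learning, "a second multivariate regression analysis will be performed with age, pre-test score, post-test scores and their interactions", followed by four named interactions. Specialty is in neither list, and no stratified or sensitivity analysis by specialty appears elsewhere. The section asks for at least 10 participants per predictor and 10 in each of four age bands (40), raised to 70 for attrition. The age bands are not crossed with specialty.

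Appendix A names the three specialties inside the item on years of practice, but has no separate field for the participant's own specialty.

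**The concern.** Age is observed, not randomised, so the baseline slope is open to confounding by anything related to both age and score. Specialty is an obvious candidate because it determines the test room and may go with different exposure to arrests. Nothing in recruitment keeps the specialty mix similar across age bands. If older volunteers came disproportionately from one specialty, part of a specialty or room difference would be read as an effect of age. If the mix were even, any specialty difference in score would still sit in the residual and widen the interval for age. The protocol expects its results to inform national policy on practice assessment, so the question will be asked.

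The term multivariate regression does not imply an unstated adjustment, since the predictors are listed.

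**Working it through.** **The plan's figures.** 4 bands x 10 = 40, which reproduces. No attrition rate is given for the step to 70; it implies 1 - 40/70 = 42.9%.

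**The plan's rule of 10 per predictor.** A three-level specialty adds two indicators.
- Baseline model: 1 + 2 = 3 predictors, so 30 participants, within 40.
- Learning model: 3 main terms + 4 interactions = 7 listed terms, already 70 participants. With specialty, 9 terms, so 90, against 70 recruited before attrition.

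**Illustrative bias.** The documents give no specialty gap in age or score, so these inputs are assumptions: two equal groups, age SD 11 years (variance 121), mean ages 4 to 6 years apart, mean scores 0.3 to 0.5 SD apart.

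Spurious slope per decade = (age gap/2 x score gap/2)/121 x 10
- Low end: (2 x 0.15)/121 x 10 = 0.025 SD
- High end: (3 x 0.25)/121 x 10 = 0.062 SD

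The standard error of the slope per decade is about 10/(11 x sqrt(n-1)): 0.11 at n=70 and 0.15 at n=40. The bias is therefore about 0.2 to 0.6 of one standard error.

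**Is a 4-year gap plausible by chance?** With two equal groups from the same age distribution, the standard error of the difference in mean age is 11 x sqrt(2/20) = 3.48 years at n=40 and 11 x sqrt(2/35) = 2.63 at n=70. A gap of at least 4 years then arises in about 25% and 13% of samples. Chance imbalance adds noise, which adjustment removes; only selective volunteering adds systematic bias.

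**Simulation** (2,000 runs per setting, two-sided 5% test; gaps in within-specialty SDs, all assumed).
- True slope zero, n=70, one specialty falling from 50% of the youngest band to 20% of the oldest: the unadjusted false-positive rate is about 7% if that specialty scores 0.5 SD higher, 9% at 0.8 SD, and 18% with specialties at +0.8, 0 and -0.8 SD. Adjusted, it is about 4 to 6%. With a milder shift (40% to 30%), the unadjusted rate is about 5 to 6.5%.
- True slope -0.3 SD per decade, specialty unrelated to age, power unadjusted against adjusted at n=70: 79% against 81% (0.5 SD), 77% against 80% (0.8 SD), 69% against 81% (+0.8/0/-0.8). At n=40 the last case is 43% against 55%.

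**Cost of adjusting.** If specialty is unrelated to age, the ratio of standard errors is sqrt((1-R2)(n-2)/(n-4)), where R2 is the share of score variance that specialty explains.
- R2 = 0: sqrt(68/66) = 1.015 at n=70; sqrt(38/36) = 1.027 at n=40.
- Break-even R2 = 2/(n-2): 2.9% at n=70, 5.3% at n=40.
- R2 = 10%: the standard error falls 3.7% at n=70 and 2.5% at n=40.

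If specialty is related to age, the cost is higher. A 6-year gap between two equal groups gives an R2 of age on group of 9/121 = 7.4%, and a further factor of 1/sqrt(1 - 0.074) = 1.039. If specialty explains nothing in the score, the total is 1.015 x 1.039 = 1.055 (n=70) or 1.027 x 1.039 = 1.067 (n=40), a rise of about 5.5% to 7%.

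**The case against.** The case for leaving the model alone has real weight.

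- The rooms are matched to specialty so that layouts are familiar, the clinical content is common, one physician from each specialty reviews the core concepts, and orientation uses a technique shared by all three. A reader might infer that the specialty-specific rooms create score differences. The documents do not support that: matching is meant to remove unfamiliarity, and no passage says that specialties differ in score or in exposure to arrests. Room and specialty also cannot be separated, so a specialty term absorbs both.
- The Background gives 32-39% of anesthesiologists over 55 and 33-40% for emergency and critical care. A reader might infer a substantial age imbalance from the age-only targets; these figures point the other way. They describe a workforce at one cut-point, however, not the volunteers who fill the 65+ band, so they make imbalance less likely without excluding it.
- Appendix A already measures crisis exposure, instructor status and simulation experience individually, and these may be better covariates than specialty. That is fair, but they are not in the model either, and specialty is the factor that fixes the test room.
- Adding specialty to the learning model breaks the plan's own rule on predictors, and the pre-test and post-test scores there should already absorb much of any stable specialty difference. This stands, and it limits the recommendation to the baseline model.

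**Conclusion.** The point holds as a minor one, for the baseline model. Specialty is absent from a non-randomised comparison in which it determines the test room and is not balanced against age. Bias requires specialty to be related to both age and score; loss of precision requires a relation to score only.

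The illustrative bias of 0.025 to 0.06 SD per decade is well under one standard error and rests entirely on the assumed gaps and age SD. The large simulated effects (18% false positives, 43% against 55% power) need specialties spread over 1.6 SD, which nothing in the documents suggests. A reader might conclude that the planned age slope is invalid, or that any age effect found would be a specialty effect. Neither follows: the documents establish the omission, not an imbalance or a score difference.

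**What to change.** 1. In the baseline model, prespecify specialty (three levels) as a fixed covariate. Report the specialty-adjusted age slope with the unadjusted slope beside it.
2. Add an explicit specialty field to Appendix A. The room used would show specialty in practice, but the questionnaire should record it.
3. In the learning model, confine specialty to a sensitivity analysis.

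The changes are a sentence or two of analysis text and one questionnaire item. The statistical price in the baseline model is 2 degrees of freedom. If specialty explains nothing, the standard error of the age slope rises about 1.5% (n=70) to 2.7% (n=40) when specialty is unrelated to age, and about 5.5% to 7% under the 6-year gap. No extra recruitment is needed for the baseline model under the plan's own rule.

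### Objective 2 is modelled only on the retention test, so immediate learning and its relation to age are not estimated, and non-returners' complete first-session data go unused for that objective

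*Combined protocol and SAP*

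**What the plan says.** Under Objectives and hypotheses, the second goal is to "Assess whether ageing influences learning from high fidelity simulation". The second hypothesis has two clauses. The first is "Although all ACP performance will improve at the immediate post-test". The second places a negative effect of age on "the retention of CRM skills 3 months following a high-fidelity simulation-based education session". The opening summary is broader: it hypothesises a negative effect of age on learning and does not mention retention.

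Under Outcome measures, the relationship of age with learning is part of the primary outcome (outcome B). It is measured by change in performance on the ACLS checklist and the Ottawa Global Rating Scale (GRS), with the note "Learning defined as improvement in performance in the simulation based crisis scenarios".

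Under Scenarios, the pre-test is followed by a 20-minute debrief, and then: "They will then manage another crisis scenario (PEA arrest once again, but with a different inciting event) as an immediate post-test". Only the retention test needs a return visit, at three months and no later than six months after the pre-test.

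Under Statistical Analysis and Sample Size Calculation, the only model for hypothesis 2 has "outcomes B on the retention test (listed above) as the dependent variables". Age, pre-test score, post-test scores and several interactions are its predictors. Loss to follow-up is addressed in one sentence: "To account for attrition, we will aim to recruit 70 participants total across both sites". No method for missing scores is described.

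**The concern.** The model answers a narrower question than the objective. It asks whether age predicts the retention score among people with the same pre-test and immediate post-test scores. It does not ask whether physicians improved after the debrief, or whether that improvement varied with age. Both fall within objective 2 and within the protocol's definition of learning, and the first is an explicit clause of hypothesis 2.

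Two things are at stake. First, an age difference in initial learning could exist and go unreported, because adjusting for the immediate post-test takes out of the age coefficient whatever acts through that test. Second, a regression has no outcome value for a participant who does not return. Everything reported on learning would then describe returners only, although the first-session pair of scores is the part of the learning data least exposed to attrition.

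**Working it through.** **Inputs from the protocol.** Four age groups of 10; recruitment target 70; three tests, two of them in the first session; one model for hypothesis 2 with a retention outcome. The protocol gives no attrition rate, effect size, standard deviation, alpha or power. Every figure below that needs one of these is labelled as assumed.

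**1. The plan's own figures.** 4 x 10 = 40, as stated. The step to 70 cannot be reproduced independently because no rate is given. Solved backwards, 70 - 40 = 30 and 30/70 = 42.9%. Assumed losses of 10, 20, 30 and 40% would have required 45, 50, 58 and 67 recruits to leave 40.

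**2. What each participant contributes under the stated models.**

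| Tests completed | Hypothesis 1 model | Hypothesis 2 model | Pre-to-immediate-post change |
|---|---|---|---|
| All three | yes | yes | observed, not analysed as an outcome |
| First session only | yes | no (no outcome value) | observed, not analysed as an outcome |

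Reading outcome B as a change from pre-test to retention does not alter this. With the pre-test among the predictors, subtracting it from the outcome shifts only the pre-test coefficient by 1 and leaves the age coefficient as it was. The retention score is still required.

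**3. Precision for immediate change.** The standard error of an age slope scales as 1/sqrt(n), other things equal. The ratio of the standard error in all 70 to that in returners only is sqrt(n returning / 70):
- 10% loss (assumed), 63 return: sqrt(63/70) = 0.949, about 5% smaller with all 70
- 20% loss (assumed), 56 return: sqrt(56/70) = 0.894, about 11% smaller
- 30% loss (assumed), 49 return: sqrt(49/70) = 0.837, about 16% smaller
- 42.9% loss, 40 return: sqrt(40/70) = 0.756, about 24% smaller

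**4. What the planned age coefficient leaves out.** Take assumed standardised effects: age on the immediate post-test given pre-test, -0.20; immediate post-test on retention, 0.40; age on retention given both earlier tests, -0.20. The planned coefficient targets -0.20. The effect of age on retention given pre-test alone is -0.20 + 0.40 x (-0.20) = -0.28. The -0.08 that runs through initial learning appears nowhere in the plan's output.

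**5. Does loss bias the planned coefficient?** With the same assumed effects, 4,000 simulated trials of 70 with 40 returning, and lower return among older and lower-scoring participants, the planned main-effects age coefficient averaged -0.20 in all 70 and -0.20 in the 40 returners. Its standard deviation across trials was 0.11 and 0.15. Under that assumption the cost is precision, not bias.

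**6. Which form the added analysis should take.** Assume a baseline age slope of -0.20 per decade, a slope of immediate gain of -0.15, and equal person and residual standard deviations of 0.7. Pre-test reliability is then 0.49/(0.49 + 0.49) = 0.5.
- Change score on age: -0.15, the gain slope itself.
- Post-test on age and pre-test: the post-test slope on age is -0.20 - 0.15 = -0.35, and the age coefficient is -0.35 - 0.5 x (-0.20) = -0.25.

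The difference of -0.10 is half the baseline decline, counted as poorer learning because a noisy pre-test adjusts only in part.

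**The case against.** The strongest reply is that the planned model fits the hypothesis it is meant to test. Hypothesis 2 places the age effect on three-month retention and predicts no age difference at the immediate post-test. This stands for the age clause, and the retention model should stay. It does not cover the first clause of hypothesis 2, the wider wording of objective 2, or the definition of learning.

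A reader might infer that attrition biases the planned age coefficient. The documents do not support that: the model conditions on age, pre-test and post-test, and loss that depends only on these need not bias it. Nor does the added analysis restore precision to the retention model, since non-returners still have no retention score.

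A reader might also infer that the plan expects to lose 30 of 70. It states no rate and does not call 40 a minimum number of completers; 30 is a difference between two figures. That non-returners are left out is likewise an inference, drawn from the chosen outcome and the absence of any missing-data method.

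Finally, one can simulate a large distortion of the immediate-gain slope among returners. With an assumed true slope of -0.15, return driven purely by an age-by-post-test interaction gives about -0.04, but ordinary main effects of age and score on return give about -0.12. The result depends on the assumed mechanism, and the plan proposes no such returner-only analysis, so these figures do not measure harm done by the plan.

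The model also lists interactions with an undefined intervention term in a single cohort. That needs clarifying, but no reading of it changes the stated outcome.

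**Conclusion.** The point holds as a gap in coverage of a primary outcome. Followed exactly, the plan leaves the first clause of hypothesis 2 untested and the relation of age to immediate learning unestimated, and it takes nothing for objective 2 from participants who do not return.

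If losses reached the 30 that the gap between 40 and 70 leaves room for, an analysis of immediate change in all 70 would have a standard error about 24% smaller than one in 40 returners; at losses of 10 to 30% the gain is about 5 to 16%. These figures assume that the residual spread and the age distribution are the same in returners and in all participants. The conclusion that the retention coefficient is not necessarily biased rests on return depending only on age, pre-test and post-test, which cannot be verified from the data. The gap is worth closing before analysis but does not invalidate the retention model.

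**What to change.** Add to the hypothesis 2 analysis, for the GRS and the ACLS checklist, the change from pre-test to immediate post-test in everyone who completed the first session, whether or not they return. Report the mean change and its regression on age. Use the change score, since the protocol defines learning as improvement. A mixed model with age by test occasion on all available tests, with an unrestricted covariance among the three tests, serves the same purpose. Do not substitute a regression of the post-test on age and pre-test, for the reason shown in step 6.

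Keep the retention model as the test of the retention clause. Beside it, show age, pre-test and immediate post-test scores for returners and non-returners, and limit conclusions on retention to what that comparison supports.

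The cost is a few sentences and one extra analysis per instrument, on scenarios that are already to be recorded and rated. The small downside is one more age coefficient per instrument, which should be labelled as the immediate-learning component of hypothesis 2.

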Objective: This study aims to 1) investigate the impact of ACP ageing on CRM skills and 2) assess whether ageing influences CRM learning from high-fidelity simulation. We hypothesize that (i) in ACP, baseline CRM performance will decline with increasing age and that (ii) age will negatively impact CRM learning after simulation-based education.

Methods: This will be a prospective multi-center trial. Seventy participants will individually manage a simulated crisis (pre-test) to assess the baseline effect of age on CRM skills. After an instructor-led debriefing, another simulated crisis (immediate post-test) and a third simulated crisis (retention post-test) three months later. All scenarios will be video-recorded and rated by blinded raters using validated tools. Regression analysis will be performed to determine the effect of ACP's age on baseline performance and learning.

Significance: This study will be the first prospective trial to delineate the effect of ageing on CRM performance and learning in a simulated setting. The results will help shape national policy regarding practice assessment and help tailor continuing medical education.

Background

Physician demographics

The proportion of older acute care physicians (ACP) has been steadily increasing.¹ Within Canada, approximately 32% - 39% of anesthesiologists are over the age of 55. A recent survey of members of the American Society of Anesthesiologists in 2013 revealed that a greater percentage of members are older (>55) in 2013 compared to 2007. These numbers are similar for emergency and critical care physicians where the proportion of the workforce over 55 is also 33-40%.² This shift in the demographics may be explained by various factors. It can partially be attributed to the recent economic crisis leading to delayed retirement. Also, in the early 1990s, there was a reduction of residency positions, likely explaining the smaller population of middle aged ACP and hence, increasing demand for the older population to meet the needs of the healthcare system.^{3,4} Recent studies have also reported an overall shortage of healthcare providers of all ages with conditions varying by region. This is another reason for a greater number of older ACP currently working, as it calls upon delayed retirement of the older physicians to meet the demands of the healthcare system secondary to this shortage.⁵⁻⁷

Consequences of Ageing

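### The target of 40 comes from age strata, not from the retention model's predictors; if all seven listed terms are estimable, 70 recruits satisfy the plan's own rule only with no attrition

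*Combined protocol and SAP*

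**What the plan says.** All the sizing text is in the section Statistical Analysis and Sample Size Calculation. It makes adequate power depend on a ratio: "we will need at least 10 participants per predictor variable entered into the analysis". The next sentence sets the target by age band: "we will aim to recruit 10 participants per 10 year age group (<45, 45-54, 55-64, 65+), equaling 40 ACP". The total follows: "To account for attrition, we will aim to recruit 70 participants total across both sites". No attrition rate, alpha, power or effect size is given.

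The same section describes two models. The first relates baseline performance to age. The second, for hypothesis 2, is specified as follows: "a second multivariate regression analysis will be performed with age, pre-test score, post-test scores and their interactions". The interactions are then listed: "age x pre-test score, age x intervention, age x pre-test score x intervention, and pre-test score x intervention) as predictors". Its response is "outcomes B on the retention test (listed above) as the dependent variables", so only participants who come back for the third scenario contribute.

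The word *intervention* appears in three of the four interactions and is not defined. Under Scenarios, the design has a single group: "Each participant will then manage a PEA arrest scenario (pre-test) and then be debriefed on their CRM skills". The retention test takes place three months later and is allowed up to six months after the pre-test.

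**The concern.** The age bands describe how recruitment should be spread. They are not predictors: both models enter age as one variable. The plan's only power criterion is therefore stated and then not applied to either model.

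This matters most for the retention model. It has the most terms, it loses participants to follow-up, and it tests the hypothesis about age and learning, which is part of the primary outcome. As written, a reader cannot tell whether the rule is met for it. If age shows no effect on retention, the paper could describe the study as adequately powered with no stated detectable effect behind the claim. The plan intends the results to inform national policy on practice assessment, so the precision behind a null result should be visible beforehand.

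**Working it through.** **Inputs from the plan:** at least 10 participants per predictor; four age bands with 10 in each; 70 recruits; one named predictor in the baseline model; three main terms and four interactions in the retention model; every participant debriefed.

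**1. The plan's figure.** 4 × 10 = 40, which reproduces exactly, but from age bands. Going from 40 to 70 implies an attrition of 1 − 40/70 = 42.9%, a rate the plan does not state.

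**2. The rule applied to the models.** Baseline model: 10 × 1 = 10, easily met. Retention model as listed: 3 + 4 = 7 terms, and 10 × 7 = 70 completers. This counts post-test scores as one term and age as continuous.

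**3. How many of the seven terms can be estimated.** This depends on what *intervention* means.

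- If it is constant (everyone debriefed, coded 1), age × intervention equals age, pre-test × intervention equals pre-test, and age × pre-test × intervention equals age × pre-test. Four distinct terms remain: age, pre-test, post-test and age × pre-test.
- If it stands for the post-test score, all seven are distinct.

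A rank check on a simulated design matrix for 70 participants, excluding the intercept, gave 4 and 7 respectively.

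**4. Room for attrition with 70 recruits.** The loss rates below are assumptions.

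| Completers | Loss from 70 | Per predictor, 7 terms | Per predictor, 4 terms |
|---|---|---|---|
| 70 | 0% | 70/7 = 10.0 | 70/4 = 17.5 |
| 63 | 10% | 63/7 = 9.0 | 63/4 = 15.8 |
| 56 | 20% | 56/7 = 8.0 | 56/4 = 14.0 |
| 49 | 30% | 49/7 = 7.0 | 49/4 = 12.3 |
| 40 | 42.9% | 40/7 = 5.7 | 40/4 = 10.0 |

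Losses tolerated: 70 − 70 = 0 with seven terms; 70 − 40 = 30 with four.

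**5. What these numbers could detect.** A per-predictor ratio does not give power, so I computed the smallest partial correlation r detectable for one coefficient. Assumptions: two-sided alpha 0.05, 80% power, one outcome, p predictors, n completers. Two formulas were used:

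- Noncentral F with 1 and n − p − 1 degrees of freedom and noncentrality n × r²/(1 − r²).
- Fisher z: r = tanh[(1.960 + 0.842)/√(n − (p − 1) − 3)]. For n = 40 and p = 7, this is tanh(2.802/√31) = 0.465.

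| n | p | Noncentral F | Fisher z |
|---|---|---|---|
| 40 | 4 | 0.415 | 0.447 |
| 40 | 7 | 0.416 | 0.465 |
| 49 | 7 | 0.379 | 0.416 |
| 56 | 7 | 0.357 | 0.387 |
| 63 | 7 | 0.338 | 0.364 |
| 70 | 4 | 0.322 | 0.337 |
| 70 | 7 | 0.322 | 0.344 |

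**The case against.** The strongest reply is that the shortfall is conditional. In a design where everyone is debriefed, *intervention* is most simply a constant. Four terms are then estimable, the rule asks for 40, which is the plan's figure, and 70 recruits can lose 30. That is right about the arithmetic, and it is why the shortfall is stated only for the seven-term case. It does not rescue the text: the plan reaches 40 from age bands, so the agreement is a coincidence, and this reading makes three of the listed predictors redundant.

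It can also be said that the age-band target has its own stated purpose, a meaningful sample, and was never offered as the product of the rule. On that reading the rule yields no number at all, which leaves the same gap. Nor is this a slip in multiplication; the fault lies in what was multiplied.

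Three further points stand as limits.

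- Four and seven are not the only possible counts. Post-test scores, in the plural, could enter as more than one variable, and an intervention main effect or categorical age would push the requirement above 70.
- The baseline model names one predictor but does not say it is the only one, and it too lacks a stated detectable effect.
- The plan does not say which coefficient tests hypothesis 2. With product terms, the age coefficient depends on centring, so the correlations above show scale and do not describe a particular test.

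Finally, no passage says that a null result will be called adequately powered. The risk is inferred from the plan's claim to power the study adequately.

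**Conclusion.** The concern holds and should be fixed. The only stated power criterion is not applied to the models, and 40 rests on recruitment strata. If all seven listed terms are estimable, the rule needs 70 retention completers and 70 recruits allow no losses; at 40 completers the ratio is 5.7. If *intervention* is constant, the rule is met with room for 30 losses, but the model as written cannot be fully estimated. Either the stated size or the stated model needs correcting, and nothing elsewhere in the document settles which.

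Under the assumptions given, the detectable partial correlation is about 0.41 to 0.46 with 40 completers and 0.32 to 0.34 with 70. The baseline model, with age as its one named predictor, is not affected by the per-predictor count.

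**What to change.** 1. Define *intervention* for this single-group design and list the terms to be entered. If it is constant, delete the three duplicate interactions, which leaves four predictors. If it means the post-test score, write it that way, which gives seven. State whether post-test scores are one variable or more.
2. Rewrite the sample-size paragraph from that count and the expected number of retention completers, with the assumed attrition rate. If the rule is then not met, either say so or pre-specify, before scores are analysed, a model the completers can support. That choice is the sponsor's.
3. Replace the claim of adequate power with a detectable effect. Name the coefficient that tests hypothesis 2, the centring, the alpha, the power and the formula. The figures above can serve as a starting point.
4. Keep the age bands as a target for the spread of recruitment only.

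The cost is text edits and a less favourable stated figure, with no added participants, visits or data. If the sponsor chooses a smaller retention model, the omitted interactions can no longer be tested.
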